6.2.3. Other Toxicities

In addition to CRS/infusion reactions, a number of adverse events that were felt to have possible, probable, or definite relationship to flotetuzumab were observed in $\geq 10\%$ of patients enrolled in the phase I study. The most common such events included pyrexia in 27.3% of patients (Gr ≥ 3 in 3.5%); nausea in 22.7%; decreased lymphocyte count, decreased platelet count, diarrhea, and vomiting in 13.6%; and chills, fatigue, decreased white blood cell count, and hypocalcemia in 12.1%; and increased alanine aminotransferase, hypomagnesemia, and anemia in 10.6%. The following grade 3/4/5 treatment-related adverse events have been reported:

- Grade 3: infusion-related reaction (12/66, 18.2%); anemia (7/66, 10.6%); febrile neutropenia (5/66, 7.6%); and pyrexia, white blood cell count decreased, C-reactive protein increased, hypocalcemia, hypophosphatemia, pulmonary edema, hypotension, hypertension, and delirium (2/66, 3.0% each); and lymphocyte count decreased, alanine aminotransferase increased, weight increased, urine output decreased, diarrhea, syncope, hypofibrinogenemia, thrombocytopenia, arthralgia, musculoskeletal pain, joint range of motion decreased, dyspnea, laryngeal inflammation, mental status changes, hyperbilirubinemia, and infection (1/66, 1.5% each).
- Grade 4: lymphocyte count decreased and platelet count decreased (8/66, 12.1% each); white blood cell count decreased (5/66, 7.6%); neutrophil count decreased (4/66, 6.1%); and alanine aminotransferase increased, aspartate aminotransferase increased, and respiratory failure (1/66, 1.5% each).
- Grade 5: none.

7. Correlative Studies

The correlative laboratory studies will be attempted on all patients. However, they are not a requirement for participation, and are not formal study endpoints. The overarching goals of the correlative studies are to:

1. Explore the impact of MRD as measured by conventional multi-color flow cytometry (MFC), RNA/DNA-based approaches, and our group's MFC LSC assay^{54,55}, and their impact on RFS in AML patients who receive flotetuzumab following transplant.
2. Characterize the effect of flotetuzumab on allogeneic T-cells, particularly on their re-distribution, *in vivo* expansion, activation, and effector differentiation after treatment using MFC.
3. Characterize the effect of flotetuzumab on T cell receptor diversity.
4. Characterize the effect of flotetuzumab on T cell gene expression using MFC and RNA sequencing.
5. Characterize gene expression in the tumor microenvironment (TME) using the NanoString PanCancer IO360 assay, and assess the impact of TME gene expression patterns on response to therapy.⁶⁹
6. Characterize T-cell infiltration of the bone marrow using multiplex immunohistochemistry (IHC).⁷⁰

7.1. MRD Monitoring

The high relapse rate seen in adult AML following alloHSCT indicates the lack of eradication of MRD despite morphologic remission. In AML, the presence of MRD by conventional MFC is highly correlated with the expression of leukemia-specific fusion transcripts, and patients with persistent MRD prior to and following transplant have worse overall survival.²⁹ Correlative specimens will be banked to allow exploration of novel MRD assays in addition to conventional MFC. One such novel assay is a 5-gene RQ-PCR assay developed by Goswami et al. that can be run on peripheral blood samples.⁷¹ The RQ-PCR assay has previously been used to assess MRD in AML patients who underwent a MAC alloHSCT, and demonstrated 89% sensitivity and 100% specificity in predicting post-transplant relapse within one year of transplant based on the presence of MRD pre-transplant.³⁵ The RQ-PCR assay can be performed on peripheral blood samples, and it would be more convenient to use in future trials, assuming its performance is comparable to a conventional MFC assay for MRD. An additional advantage of this approach is that it does not require a baseline sample of the patient's disease, which may not be available in

this patient population. Another approach will use next generation sequencing (NGS) with a panel of 32 genes that are commonly mutated in AML as well as qPCR for NPM1, which cover approximately 82% of all AML at a sensitivity of 10^{-4} for single nucleotide variants and 10^{-5} for insertions/deletions.⁷² This DNA-based next generation sequencing (NGS) has shown a 71% concordance rate with conventional MFC, and pre-transplant MRD by NGS and MFC show a similar association with post-transplant relapse and survival.⁷³ Notably, the simultaneous presence of MRD by NGS and MFC seems to confer the greatest risk of relapse, so it will be particularly helpful to assess both simultaneously. One limitation of this approach will be the need for diagnostic samples, which may be not be available for all enrolled patient. In addition to conventional MFC, we will also use our group's MFC assay to detect LSCs from bone marrow samples.^{35,54} Our group's MFC LSC assay has been shown to be more sensitive for MRD than conventional MFC assays; this probably results from the fact that LSCs in a large fraction of patients do not express the same antigen aberrancy as more differentiated progeny.^{54,55,74}

7.2. Flow Cytometry Studies

We will perform multi-color flow cytometry on PB and BM specimens before and after flotetuzumab using three pre-determined panels of mAbs including but not limited to those specific for CD3, CD4, CD8, PD-1, CD45RA, CCR7, CD25, CD27, CD28, CD69, Ki-67, T-bet, CD127, FoxP3, HLD-DR, CTLA-4, TNFRII, TIM3, LAG-3, CD160, 2B4, BTLA, KLRG-1, CD16, and CD56. This multi-color approach allows the examination of different CD4⁺ and CD8⁺ T cell subpopulations (expressing CD45RA, CCR7, CD27, and CD28), phenotypic separation of human CD4+FOXP3+ T cells into three distinct subpopulations, and assessment of their proliferative status (% Ki-67 cells).^{75,76} The expression of CD69, HLA-DR and TNFRII will be measured to characterize T cell activation status and the expression of co-inhibitory molecules (PD-1, TIM3, LAG-3, CD160, 2B4, BTLA, and KLRG-1) will be studied. Natural killer cells (NK), NK-T cells will be enumerated using CD16 and CD56 (NK/NK-T cells).

7.3. Immune Profiling of the T cell repertoire

The studies proposed will evaluate the T cell receptor (TCR) diversity in T cells isolated from PB and BM from patients before and after treatment with flotetuzumab. We will determine TCR diversity and clonal composition using a molecular and computational approach based on high-throughput DNA sequencing of rearranged TCR β CDR3 regions from T cell genomic DNA. This approach allows direct measurement of the TCR β CDR3 region sequence diversity in any

arbitrarily complex population of T cells and also permits quantitative description of the clonal composition of the population.⁷⁷ The [name] laboratory in collaboration with the [name] laboratory from the Fred Hutchinson Cancer Research Center (FHCRC) has performed extensive monitoring and tracking of the TCR repertoires in patients undergoing alloHSCT (manuscript in preparation). We are utilizing an established multiplex PCR strategy to amplify the CDR3 region of the TCR, spanning the variable region formed by the junction of the V, D, and J segments and their associated non-template insertions followed by Illumina-based sequencing methodology, a well-characterized methodology developed by Adaptive Technology (<http://www.adaptivebiotech.com/technology/>). Sequencing is followed by comprehensive bioinformatics analyses focused on determining the diversity of the T cell and B cell repertoires as well as the entropy and clonality of each repertoire consistent with previous studies. Through these ongoing studies we have developed substantial experience not only in using and analyzing DNA retrieved from unsorted PBMCs but also from sorted T cell subpopulations (naïve vs. memory vs. regulatory), paired PB and BM samples as well as DNA retrieved from FFPE archived tissues.

We hypothesize that a primary action of flotetuzumab will be to re-direct allogeneic T cells toward the CD123+ cells resulting in increased TCR diversity and the emergence of unique TCR clonotypes that may be relevant in allogeneic post-transplant anti-tumor immunity. The long-term goal of this correlative work is to uncover biomarkers that predict which patients will respond to flotetuzumab. This correlative work will also provide deeper insight into allogeneic anti-tumor immunity, effects of anti-CD123/CD3 mAbs on GVHD, and mechanisms of failure to eradicate anti-CD123+ malignancies after flotetuzumab treatment. Exploratory studies to characterize T cell transcriptional signature before and after treatment using Human Prime View Gene Expression Array (<http://www.affymetrix.com>) will be also considered to gain further insight into T cell function in patients with AML before and after treatment. While analysis will focus on CD8⁺ T cells, as part of T cell isolation we are routinely sorting CD8⁺, CD4⁺, B cells, NK cells and tumor cells; these other populations will be stored for future analysis if of interest.

7.4. Cytokine Profiling

As a part of PB and BM collection and mononuclear cell isolation we will collect plasma that will be used for the measurement of defined cytokines (IL-2, IL-6, IL-10, IFN- γ , TNF- α) to assess flotetuzumab and checkpoint inhibitors-induced global T-cell activation. We will examine the levels of cytokines before and after treatment with flotetuzumab.

7.5. Operating Procedures for Specimen Collection

Peripheral blood and bone marrow specimen collection will be performed as delineated in the study calendar (Section 4.3) and shown in Figure 2. Correlative studies will only be collected at the times when peripheral blood and bone marrow collections are performed for clinical care. All enrolled patients will have bone marrow and peripheral blood samples collected prior to treatment with flotetuzumab (day -14-0), following treatment with flotetuzumab (day 28), at days 180 and 365 post-transplant, and at the time of relapse as illustrated in **Figure 2**. An additional peripheral blood sample will be collected during the first cycle of treatment with flotetuzumab on day 14.

[figure not shown]

Figure 2: Sample Collection for post-transplant flotetuzumab

Bone marrow: 5 x 8mL will be collected in green top ACD tubes (~40 mL). Re-adjustment of the direction of bone marrow aspirate needle should take a place after each 10 cc is collected to prevent hemodilution. At the time of collection, green top tubes must be thoroughly mixed to prevent clotting.

Peripheral blood: 5x8mL ACD green top tubes of blood (~40mLs) will be collected at each time point.

Specimens should be labeled with the patient's study number (given at the time of registration), study protocol number, sample collection date and time, and sample source (PB or BM). Thus, the samples will be de-identified, but the principal investigator and relevant study staff will have access to the study numbers to allow clinical correlation. Sample collection date and time, and sample source (PB or BM) will be recorded. All data should be kept in the laboratory log. At each sampling time, BM and PB mononuclear cells (PBMC) will be processed via Ficoll density gradient centrifugation. The washed cells will be counted, triaged for DNA isolation, and viably

cryopreserved using a controlled-rate freezer with transfer to the vapor phase of liquid nitrogen for long-term storage.

The specimens should be delivered to the [name] Laboratory at the Sidney Kimmel Comprehensive Cancer Center immediately after collection. Members of the [name] Laboratory will have access to the de-identified samples for the purposes of the studies outlined herein. Analysis of the results including correlation with clinical information will be performed at the Sidney Kimmel Comprehensive Cancer Center. Upon completion of the research protocol (i.e. two years from the end of treatment of the final patient), all specimens will be destroyed or transferred to the Johns Hopkins Biospecimen and Genomic Data Bank in the Department of Pathology based on the patients' agreement.

8. Statistical Methods

This is a pilot study of flotetuzumab in patients with AML as post-alloHSCT therapy among patients in remission and those with relapsed disease.

8.1. Endpoints

8.1.1. Primary Endpoints

1. Adverse events and toxicities will be tabulated and reported by type and grade and the proportions reported with exact 95% binomial confidence intervals.
2. The maximum tolerated dose (MTD) of flotetuzumab in patients with relapsed/refractory AML following alloHSCT will be determined.

8.1.2. Secondary Endpoints

8.1.2.1. Response-related Endpoints

- 1) Report the complete response (CR + CRi) rate in relapsed AML to flotetuzumab following alloHSCT.

8.1.2.2. Toxicity-related Endpoints

- 2) Report the incidence of acute GVHD
- 3) Report the incidence of chronic GVHD
- 4) Report cumulative incidence of non-leukemia mortality

8.2. Study Design

This study proposal will be a phase 1 trial of flotetuzumab in patients with relapsed/refractory AML following alloHSCT. The first part of the study will be a dose escalation following a 3+3 design for post-transplant flotetuzumab. The study will start with the recommended dose of flotetuzumab in relapsed/refractory ALL (DL1). The first three patients will be enrolled and monitored for the first cycle of treatment for DLTs through the full DLT period (90 days) before enrolling additional patients. If less than 2 patients experience a DLT, an additional 3 patients will be enrolled. If 0 or 1 out of 6 patients have a DLT, then the dose will be deemed safe and considered the MTD of flotetuzumab in the post-transplant setting. If 2 or more of the first 3 or 6 patients experience a DLT, then the trial will proceed to enroll patients at DL-1 starting with 3 patients. The first three patients on DL-1 will be enrolled and monitored in the first cycle of treatment for DLTs through the full DLT period (90 days) before enrolling additional patients. If less than 2 patients experience a DLT at DL-1, an additional 3 patients will be enrolled at DL-1. If 0 or 1 out of 6 patients have a DLT at DL-1, then the dose will be deemed safe and the MTD. If 2 or more of the first 3 or 6 patients experience a DLT, then the trial will be stopped. An expansion cohort of 4 subjects will be also pursued at MTD for flotetuzumab to further characterize safety, tolerability and any preliminary signs of biological or clinical activity in this cohort. DLT monitoring will continue in this expansion cohort, and the trial will be stopped if two additional subjects experience a DLT. Any patient who discontinues treatment prior to the completion of one cycle of flotetuzumab for disease progression or for an adverse event that is not possibly, probably, or definitely due to the study treatment will be replaced.

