1.1. Primary Objective

Define the maximum tolerated dose (MTD) of flotetuzumab in patients with relapsed/refractory AML following alloHSCT.

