4.2. Treatment Schedule

All patients will undergo a bone marrow biopsy prior to enrollment to assess for relapse and must have gross morphologic evidence of relapsed leukemia ($\geq 5\%$ blasts) for enrollment in this group. Patients may enroll at any time after day +30 post-transplant. Patients enrolled on DL1 will receive flotetuzumab by continuous infusion using multi-step lead-in dosing as outlined in

Table 1, and then 500 ng/kg/day on days 7-28. After one cycle, all patients will undergo a bone marrow biopsy to assess response including assessment of MRD. Patients who fail to achieve a CR, CRI, CRh, or MLFS may continue with subsequent induction cycles as a continuous infusion up to a total of five cycles. If there is evidence of response (CR, CRI, CRh, or MLFS) and the toxicities of treatment are acceptable, patients will be eligible for two consolidation cycles as outlined in Table 1. Additional bone marrow biopsies for response assessment will be performed after the second cycle. Results will be censored should patients undergo a second alloHSCT. If there is a need to de-escalate dosing based on toxicity, then patients will be enrolled on DL-1 using multi-step lead-in dosing as outlined in Table 1, and then 300 ng/kg/day on days 5-28 of the first cycle and days 1-28 of subsequent cycles.

Table 1			Dosing Schedule	
Cycle	Week	Days	ng/kg/day	
Induction: Cycle 1				
1	1	Day 1	DL1	DL-1
		Day 2	30	30
		Day 3	60	60
		Day 4	100	100
		Day 5	200	200
		Day 6	300	300
		Day 7	400	300
	2	Days 8-14	500	300
	3	Days 15-21	500	300
	4	Days 22-28	500	300
Consolidation/Reinduction: Cycle 2 and beyond				
2	1	Days 1 – 28	500	300

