4.3 Flotetuzumab Dosing

Flotetuzumab dosing in this trial will be based on maximum tolerated dose schedule as determined in the phase I trial and subsequently modified with multi-step lead-in dosing during the first week of treatment.^{60,61} During week 1 of treatment, patients will receive flotetuzumab via continuous infusion using multi-step lead-in dosing as described in table 1. If they tolerate this lead-in dose, then they will be escalated to a dose of 500 ng/kg/day on days 7-28 for DL1 or

300 ng/kg/day on days 5-28 for DL-1. Dosing in subsequent cycles will be as outlined above without multi-step lead-in dosing.

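### If DL1 clears, the trial shows that DL1 met the tolerability rule, not that DL1 is the maximum tolerated dose after alloHSCT

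*Combined protocol and SAP*

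**What the plan says.** The primary objective in section 1.1 is: "Define the maximum tolerated dose (MTD) of flotetuzumab in patients with relapsed/refractory AML following alloHSCT". The second primary endpoint in section 8.1.1 repeats it: "The maximum tolerated dose (MTD) of flotetuzumab in patients with relapsed/refractory AML following alloHSCT will be determined". The first primary endpoint there tabulates adverse events and toxicities, with exact 95% binomial intervals for the proportions.

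Section 8.2 describes the design in these words: "The first part of the study will be a dose escalation following a 3+3 design for post-transplant flotetuzumab". Sections 4.2 and 4.3 and Table 1 contain two levels: DL1 (500 ng/kg/day after lead-in) and DL-1 (300 ng/kg/day after lead-in). Enrolment starts at DL1. Section 4.2 says when the other level is used: "If there is a need to de-escalate dosing based on toxicity, then patients will be enrolled on DL-1".

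The rules in section 8.2 are:
- **0 or 1 DLT in six at DL1:** "then the dose will be deemed safe and considered the MTD of flotetuzumab in the post-transplant setting".
- **2 or more DLTs among the first three or six at DL1:** the trial moves to DL-1 and applies the same rule. It stops if DL-1 also fails.
- **After an MTD is named:** four more patients are treated at that dose, and the trial stops if two of them have a DLT.

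Section 8.3.1 caps the trial at 16 patients, and Table 7 gives 10 as the most at one level. Sections 2.9 and 4.3 say where the DL1 dose comes from: it was the MTD schedule of the earlier flotetuzumab trial, later modified with multi-step lead-in dosing.

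**The concern.** A maximum tolerated dose is a boundary. To locate it, a trial needs a dose that passes and a higher dose that does not. This design can supply both only if DL1 fails and DL-1 passes. In its most favourable outcome, where DL1 passes, nothing above DL1 has been given, so the trial's own data bound the tolerable dose from below only.

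The label also behaves oddly. The less toxic DL1 is, the more room there may be above it, and the more surely the rule calls it the maximum.

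At stake is the headline claim. A result of, say, 0/6 would be reported as the MTD in the post-transplant setting, and readers would take that as a ceiling estimated in this population. The protocol itself gives reasons not to assume that the earlier ceiling carries over. Section 2.10 says the drug has not been specifically studied in AML after bone marrow transplant. Section 2.9 links the severity of cytokine release syndrome to circulating CD4+ T cells, which it says are reduced for at least a year after transplant. Section 6.2.1 counts GVHD during treatment as a DLT. Tolerability could therefore differ from the earlier trial in either direction.

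**Working it through.** **1. Reproduce the plan's sample size and see what it contains.** From section 8.2: six at DL1, six at DL-1 and four in the expansion.

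- Total: 6 + 6 + 4 = 16, the maximum in section 8.3.1.
- One level: 6 + 4 = 10, the N in Table 7.

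Both figures reproduce, and neither leaves room for a cohort above DL1. Section 6.1 agrees, because dose preparation covers 30 to 500 ng/kg/day. The rise during the first week of cycle 1 is lead-in dosing within a patient, not escalation between cohorts.

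**2. Compare the plan's label with what each outcome supports.**

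| Outcome | Plan's label | What this trial's data support |
|---|---|---|
| DL1: 0–1 of 6 | DL1 is the MTD | DL1 met the rule; no upper limit observed |
| DL1 fails, DL-1: 0–1 of 6 | DL-1 is the MTD | One studied level passes and the next one up fails; the label is reasonable |
| Both fail | Trial stops | No studied level met the rule |

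Only the first row is at issue.

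**3. How often the rule names DL1 the MTD.** Let p be the true DLT rate at DL1. The documents state no target rate, so the values of p are assumptions. I take six evaluable patients (after replacement) with independent outcomes. A total of at most 1 in six implies at most 1 in the first three, so the two-stage path reduces to

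P(X ≤ 1) = (1 − p)^6 + 6p(1 − p)^5.

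The expansion is completed without stopping if at most one of four has a DLT:

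P(Y ≤ 1) = (1 − p)^4 + 4p(1 − p)^3.

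| Assumed p | DL1 named the MTD | Expansion completed | Both |
|---|---|---|---|
| 5% | 0.967 | 0.986 | 0.954 |
| 10% | 0.886 | 0.948 | 0.839 |
| 20% | 0.655 | 0.819 | 0.537 |
| 30% | 0.420 | 0.652 | 0.274 |

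For example, at p = 20%: 0.2621 + 0.3932 = 0.655.

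**4. Precision of the DLT rate when DL1 clears.** With no events, the exact two-sided 95% upper limit is 1 − 0.025^(1/n). For n = 10 this is 0.308. If the expansion is completed, the count can be at most 1 + 1 = 2 of 10.

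| DLTs | Exact 95% interval |
|---|---|
| 0/10 | 0–31% |
| 1/10 | 0.3–44.5% |
| 2/10 | 2.5–55.6% |

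At the moment DL1 is named, before the expansion, the intervals are wider: 0–46% for 0/6 and 0.4–64% for 1/6.

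**The case against.** The best defence is that the plan is transparent. The rule in section 8.2 is explicit, so MTD can be read as the highest pre-specified level that meets it. Sections 2.9 and 4.3 openly say that the dose was the MTD schedule of an earlier trial. On this view the trial asks whether a known MTD holds up in a new setting, with one fallback level, and the complaint is about terminology.

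Much of that stands. Starting at an established dose with a step down is an understandable choice, and no decision in the trial is wrong because of it. However, the plan never writes that definition of MTD and never says that the earlier MTD serves as the upper bound here. An outside ceiling is evidence, but its transfer to post-transplant patients is an assumption, and sections 1.1 and 8.1.1 promise a determination.

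A reader might infer more than the documents support:
- **That 97% or 89% is the chance of a wrong label.** It is the ordinary pass probability of the rule. An error rate would need a target DLT rate and a dose–toxicity curve, and the plan gives neither. Nor is a nearly non-toxic DL1 the evident case: section 6.2.3 reports related grade 3 infusion-related reactions in 12/66 (18.2%), although section 6.2.1 does not count grade 3 reactions that are managed and resolve within 72 hours.
- **That tolerability will rest on six patients.** The expansion brings the selected dose to as many as ten.
- **That exact intervals are missing.** The first primary endpoint already promises them for toxicities; only the DLT rate is not named.
- **That the earlier trial excluded transplanted patients.** Section 2.9 describes relapsed/refractory AML or intermediate/high-risk MDS and does not say this.

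**Conclusion.** The point holds for the branch in which DL1 clears. There the data show that DL1 met the tolerability rule. They do not establish that it is the maximum tolerated dose after alloHSCT, because no higher dose is studied and the ceiling comes from another trial. How often this branch occurs depends on an unknown DLT rate; over assumed rates of 5% to 30% it runs from 97% down to 42%. The structural conclusion does not depend on those rates. It needs only the two dose levels and the rule in section 8.2.

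The point does not apply if DL1 fails and DL-1 clears. It is also not an argument for testing a higher dose or for changing any dose, cohort or stopping rule. It concerns what the primary result may be called, which is worth settling before results exist.

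**What to change.** Change the wording of sections 1.1, 8.1.1 and 8.2:

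1. State the primary objective as determining whether DL1, or failing that DL-1, is tolerable in AML after alloHSCT.
2. If DL1 clears, report: *DL1 tolerated; MTD not reached within the doses tested*. At minimum, define MTD expressly as the highest studied dose meeting the rule, and say that no higher dose was tested.
3. Use MTD without qualification only if DL1 fails and DL-1 clears.
4. In section 8.2, replace dose escalation with dose de-escalation.
5. Under the first primary endpoint, name the DLT rate at the selected dose, with the expansion cohort included (up to N = 10), among the proportions already reported with exact 95% intervals.

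Doses, cohorts and decision rules are unchanged. The cost is a more modest headline claim.

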4.7.5. GVHD

If a patient develops definitive evidence of acute GVHD⁶⁶, flotetuzumab will be permanently discontinued. Study therapy will be permanently discontinued should a patient develop definitive evidence of chronic GVHD.⁶⁷ See appendix for specific GVHD assessment criteria.

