6.2 Toxicity

6.2.1. Definition of Dose-Limiting Toxicity

DLT will be defined employing the National Cancer Institute Common Terminology Criteria for Adverse Events, Version 5.0 (CTCAE v5.0), except IRR/CRS which will be defined by the modified criteria proposed by ASCT and described in section 4.7.1 and in Table 4.

DLT is defined as:

- Grade 4 neutropenia lasting \geq 42 days from start of cycle in absence of evidence of active AML (< 5% blasts).
- The development of acute or chronic graft-versus-host disease during treatment
- Grade 3–5 nonhematologic toxicity that is possibly, probably or definitely related to the study drug

EXCEPT:

- Grade 3 fatigue, asthenia, fever, anorexia, or constipation
- Grade 3 nausea, vomiting or diarrhea not requiring tube feeding, total parenteral nutrition, or requiring or prolonging hospitalization;
- Infection, bleeding, or other expected direct complication of cytopenias due to active underlying disease;
- Grade 3 or 4 tumor lysis syndrome (TLS) or disseminated intravascular coagulopathy (DIC) if it is successfully managed clinically and resolves within 7 days without end-organ damage;
- Grade 3 or 4 isolated electrolyte abnormalities (i.e., those occurring without clinical consequence) that resolve, with or without intervention, to Grade 2 levels in < 72 hours will not be considered DLT.
- Grade 3 CRS/IRR that is successfully managed and resolves within 72 hours, as this is an expected event that does not require permanent treatment discontinuation
- Any non-leukemia-related death occurring within 90 days of treatment initiation

Treatment discontinuation for adverse events prior to the completion of one cycle will be considered a DLT unless the adverse event is disease progression, which necessitates alternative therapy, or the adverse event is not possibly, probably, or definitely due to the study treatment. Patients who discontinue treatment prior to the completion of one cycle for progressive disease or due to an event that is not possibly, probably, or definitely due to the study treatment will be replaced.

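### GVHD in cycle 1 judged unrelated to flotetuzumab is a listed DLT under section 6.2.1 but a replaceable patient under sections 6.2.1 and 8.2, and the plan does not say which rule governs the MTD count

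*Combined protocol and SAP*

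**What the plan says.** Four provisions of the combined protocol and SAP meet on this point.

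- **DLT list, section 6.2.1.** One item is "The development of acute or chronic graft-versus-host disease during treatment". It carries no grade threshold and no attribution condition. The next item, Grade 3–5 events, is limited to "nonhematologic toxicity that is possibly, probably or definitely related to the study drug".
- **Discontinuation, section 4.7.5.** "If a patient develops definitive evidence of acute GVHD⁶⁶, flotetuzumab will be permanently discontinued". The same section applies the same consequence to definitive chronic GVHD.
- **Early discontinuation and replacement, end of section 6.2.1.** Stopping for an adverse event before one cycle is complete is a DLT, except for disease progression or where "the adverse event is not possibly, probably, or definitely due to the study treatment". Patients who stop early for progression or "due to an event that is not possibly, probably, or definitely due to the study treatment will be replaced".
- **Design, section 8.2.** The replacement rule is repeated for any patient who stops before completing one cycle, including "for an adverse event that is not possibly, probably, or definitely due to the study treatment will be replaced". The decision rule is "If 0 or 1 out of 6 patients have a DLT, then the dose will be deemed safe and considered the MTD"; two or more DLTs in the first 3 or 6 patients fail the dose.

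Section 9.9 defines the attribution categories. None and Unlikely fall below Possible, so they are the ratings that trigger replacement.

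**The concern.** A patient with definitive GVHD in cycle 1 must stop treatment, and so becomes an early discontinuation for an adverse event. If the investigator rates that GVHD None or Unlikely, the DLT list makes the patient a DLT, while the replacement sentences make the patient someone to be replaced. No text ranks one rule above the other.

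The conflict sits in the primary decision. The primary objective (section 1.1) is the MTD after alloHSCT, and GVHD is the transplant-specific item in the DLT list. With a cut between 1 and 2 DLTs in 6 patients, the handling of a single patient can matter. An error can go only one way: replacing a GVHD case can lower the DLT count but never raise it. If the question is settled only after a case has occurred, it will be settled with the outcome known.

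**Working it through.** **1. The plan's own numbers.** Two dose levels of 6 plus an expansion cohort of 4 give 6 + 6 + 4 = 16, the stated maximum. One level plus expansion gives 6 + 4 = 10, the N in Table 7. The plan states no operating characteristics for the 3+3 rule and no expected DLT or GVHD rate, so there is no error rate to reproduce.

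**2. The rules side by side, for GVHD leading to discontinuation before cycle 1 is complete.**

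| Attribution (9.9) | DLT list (6.2.1) | Replacement rule (6.2.1, 8.2) |
|---|---|---|
| Possible, Probable or Definite | DLT | Not replaced |
| None or Unlikely | DLT | Replaced |

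The second row is the conflict. It needs no assumed rate.

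**3. Acceptance probability.** The dose clears if X ≤ 1, with X ~ Binomial(6, p):

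P(cleared) = (1−p)^6 + 6p(1−p)^5.

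The look after 3 patients changes nothing, because at most 1 of 6 implies at most 1 of the first 3. At p = 10%, 20%, 30% and 40% this gives 0.886, 0.655, 0.420 and 0.233.

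**4. Effect of replacement.** Let r be the probability of another DLT, g of cycle 1 GVHD, and u the share of GVHD rated unrelated. All three are assumptions.

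*GVHD and other DLTs mutually exclusive.*
- All GVHD counted: p = r + g.
- Unrelated GVHD replaced and uncounted: p′ = (r + g(1−u)) / (1 − gu).
- With r = 0.15, g = 0.20, u = 0.5: p = 0.35 and P(cleared) = 0.32; p′ = 0.25/0.90 = 0.278 and P(cleared) = 0.47.

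*GVHD and other DLTs independent, replacing only patients with no other DLT.*
- p = 1 − (1−r)(1−g) and p′ = (p − x)/(1 − x), with x = gu(1−r).
- Same inputs: p = 0.32 and P(cleared) = 0.38; x = 0.085, p′ = 0.235/0.915 = 0.257 and P(cleared) = 0.52.

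**5. Range (mutually exclusive form).**

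| r | g | u | Rise in P(cleared) |
|---|---|---|---|
| 10–20% | 10% | 10% | about 0.02 |
| 10–15% | 5% | 25% | about 0.025 |
| 20% | 10% | 25% | 0.04 |
| 15% | 20% | 50% | 0.15 |
| 10% | 30% | 100% | 0.56 |

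The last row needs every GVHD case to be rated unrelated.

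**6. Single-cohort example.** Suppose two of the first three patients have cycle 1 GVHD rated Unlikely. Counted, DL1 fails at once. Replaced and uncounted, DL1 continues with no DLT from either.

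**The case against.** The strongest reply is that the text can be read without conflict. The DLT list stands on its own. The closing paragraph of 6.2.1 adds a further route to a DLT, and its exception limits only that route. Section 8.2 counts patients who experience a DLT, and a patient with GVHD has done so. This is a sensible reading and may be the intent. But the replacement sentences have no carve-out, and the one in 8.2 covers any patient, so the reading has to be supplied by whoever applies the rule.

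A reader might infer several stronger claims that the documents do not support:

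- **That the plan excludes GVHD from the DLT count, or targets the DLT rate among patients without unrelated GVHD.** The text never says a replaced patient's DLT is discarded. That is the ordinary 3+3 meaning of replacement, but here it is an inference.
- **That most post-transplant GVHD would be rated unrelated because a competing cause is always present.** Section 9.9 assigns Possible when a plausible pharmacological chain exists and another cause is just as likely. Unlikely needs more than a competing cause, such as one that is much more probable. Flotetuzumab activates T cells (sections 2.8 and 6.1), so much on-treatment GVHD could be rated at least Possible.
- **That one replacement always reverses the decision.** It does so only when there are exactly 2 DLTs and the replacement patient has none.
- **That GVHD would go unreported.** Acute and chronic GVHD are secondary endpoints (8.1.2.2), analysed with death as a competing risk (8.3.2) and with no attribution filter. DLT monitoring also continues in the expansion cohort, although the same ambiguity applies there.

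The scope is also limited. GVHD that arises after cycle 1 but within the 90-day DLT period is not subject to replacement.

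**Conclusion.** The concern holds as a conflict between written rules in the primary MTD decision. Cycle 1 GVHD that leads to discontinuation and is rated None or Unlikely is a DLT under one sentence and replaceable under another, and nothing says how it enters the 0–1 of 6 rule. If such patients are replaced and uncounted, the bias is always toward clearing the dose.

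The size cannot be fixed from the documents. In the illustrative case the probability of clearing the dose rises from 0.32 to 0.47, or from 0.38 to 0.52 under independence. It rises by only about 0.02 when GVHD is uncommon and seldom rated unrelated. The large effects need most or all GVHD to be rated unrelated, which section 9.9 makes hard to expect. The case for correction therefore rests on the text and on the direction of the bias, not on a particular figure.

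**What to change.** Reconcile sections 4.7.5, 6.2.1 and 8.2 on counting. State in 6.2.1 and 8.2 that a patient who meets any listed DLT criterion, including GVHD (listed in 6.2.1 without an attribution condition), is evaluable, is counted as a DLT, stays in the cohort denominator and is not replaced. State also that replacement applies only to patients who have not met a DLT criterion, and that both statements cover the expansion cohort. Do this before any cohort decision.

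The cost is a sentence or two in two sections. No patients are added, and neither dosing nor the discontinuation rule changes. The small downside is that some GVHD unrelated to the drug will count against the dose, which the DLT list already accepts.
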